5.4 Information for participants

5.4.1 Investigator information and training

At the initiating visit at the trial site, both GP and one HCA per practice, are trained in documentation. HCA will participate in order to be in a position to support data documentation and to carry out the Mini-Mental Status Test (MMSE). GP will be informed about the study protocol, ethical considerations and the recommended standard, and will be trained in the use of the Cumulative Illness Rating Scale (CIRS).

Content:

1. Introduction to the PRIMUM trial
2. Introduction to the execution of the trial
3. Introduction to “recommended standards“ (Geriatrics guideline, parts I and II by the Hesse guideline group¹)
4. Explanation of patient clarification, information and declaration of consent
5. Training in execution of MMSE and CIRS-appraisals
6. Introduction to trial documentation including CRFs
7. Content and execution of patient survey
8. Data monitoring, query management and reminder mechanism

9. Presentation of exact trial procedure including timeline
10. Investigators' participation agreement

5.4.2 Patient information and declaration of consent

When the patients in the random list appear in the practice, the GP in person will conduct a patient briefing with them with the help of the patient information sheet prepared for the trial. Patients are to be informed of the aims and the content of the trial, the times, the methods and the content of data collection, the random selection either for the intervention or the control group, of the intervention itself, and on data protection. The patient will be expressly advised of the fact that participation is voluntary and on the possibility to withdraw ones consent. Consent to participate in the trial, as well as the declaration on data protection should be signed and dated by the patient himself. The originals will be sent to the IGP via telefax and archived in the investigator's file. In addition to the time, date and duration of the briefing, the trial number and trial abbreviation should also be entered into the patient's medical records. The patient will receive the patient information sheet and dated and signed copies of his declaration of consent and declaration on data protection.

6 RANDOMISATION AND ALLOCATION CONCEALMENT

Practices will be randomly allocated to the complex intervention or control arm in the ratio of 1:1. Block randomisation with randomly varying block sizes will be used to provide treatment groups of approximately equal size. Randomisation lists will be provided by the Institute of Medical Biometry and Informatics at the University of Heidelberg, using computer generated numbers. Practice allocation to treatment groups will be performed by central randomisation by a study-independent researcher at the IGP after registration of the first patient per practice. Once a practice has been randomised, all the patients recruited for the practice will be deemed intervention or control depending on which arm of the study each practice was allocated. After completion of the baseline documentation of all study patients per practice, the study-independent researcher at the IGP will inform the study team at the IGP about the practice status as either intervention or control. The study team will send a fax with the randomisation result to the practice.

7 TREATMENT PLAN FOR INTERVENTION AND CONTROL GROUPS

7.1 Description of trial treatment in the intervention arm

For detailed intervention see appendix B (handed out merely to the intervention group at the time of the intervention training to avoid contamination of the control group).

As a "recommended standard", the practices in the intervention group will receive the short form of the current geriatrics guideline, parts I and II, published by the Hessen guideline group.¹

7.2 Description of treatment in the control arm

For the duration of the trial, the patients in the control group will continue to receive the usual treatment from their GP.

As a “recommended standard”, the practices in the control group will receive the short form of the current geriatrics guideline, parts I and II, published by the Hessen guideline group.¹

8 OUTCOME ASSESSMENT

8.1 Outcome measures

8.1.1 Primary Outcome

The primary outcome is the change in the appropriateness of prescriptions after 6 months follow-up measured as a difference in the Medication Appropriateness Index (MAI)-Score 6 months from baseline minus baseline (MAI T1–T0).

The criterion appropriateness of the medication will be calculated and evaluated on the basis of the *Medication Appropriateness Index* (MAI).^{30,31}

- The MAI by Hanlon et al. consists of 10 items: (1) Is there an indication for the drug?, (2) Is the medication effective for the condition?, (3) Is the dosage correct?, (4) Are the directions correct?, (5) Are the directions practical?, (6) Are there clinically significant drug-drug interactions?, (7) Are there clinically significant drug-disease/condition interactions?, (8) Is there unnecessary duplication with other drug(s)?, (9) Is the duration of the therapy acceptable?, (10) Is this drug the least expensive alternative compared to others of equal utility? The rating will take place on a three point scale whereby “1” represents the best rating (expressed as correct, practicable etc. depending on the question), “3” the worst rating (incorrect, impracticable etc. depending on the question) and “2” a middle rating. As an alternative, it is also possible to respond with “not applicable” or “unknown”.
- The MAI will be used in the following modifications that are comparable to modifications by others.^{30,32-34}
 - o Item (10) will not be rated, since this is not possible under the current conditions of discount contracts between pharmaceutical industries and different statutory health insurance companies in Germany. They are based on § 78 Abs. 3 Arzneimittelgesetz (A) and § 130a Absatz 8 SGB V (B). Both paragraphs describe the possibility to offer discounts on official prices of pharmaceuticals by pharmaceutical industry. In conclusion “best prices” vary between health insurance companies and over time.
 - o Ratings are specifically defined for each item, e.g. items (5) and (6) are limited to the most commonly observed combinations of drug-drug and drug-disease interactions, and current symptoms (taken from the telephone interview) will be considered for assignment. Operationalisation is summarised in a referenced manual (Appendix A).
- The MAI showed good intra-rater reliability for well-experienced pharmacologists.^{30,33,35-37} In [name] trial group, an MAI Rating will be carried out independently

of the project and blinded for the patient's group allocation (intervention vs. control). In a random sample of about 20% of the cases an independent second MAI rating will be carried out.

Changes of the medication regime (1) are recommended stepwise³⁸ and (2) are assumed to be in primary care not always realised by the patient immediately (pers. comm. practice advisory board). Reasons for the delay of changes in the medication taken by the patients probably rely on the prescribing behaviour for the chronically ill (large package sizes) and on financial constraints of the patients (extra out-of-pocket payments per package). Based on (1) and (2) an estimated delay of three months to implement prescriptions into taking is reasonable. To ascertain the effectiveness of the intervention the MAI should be appraised at least three months after intervention, therefore.

8.1.2 Secondary Outcomes

(1) Change in the appropriateness of prescriptions after 9 months follow-up measured as the difference in the Medication Appropriateness Index (MAI)-Score 9 months from baseline minus baseline (MAI T2–T0): To study late intervention effects a second interval will be measured for the medication appropriateness at T2 (9 months after baseline). Furthermore, treatment effects on each MAI item will be determined.

The following parameters will be determined in order to identify treatment effects on patient related outcomes:

(2) Change in generic health related quality of life measured as the difference in the EQ-5D-Score^{39,40} 6 months from baseline minus baseline (T1–T0) and 9 months from baseline minus baseline (T2–T0): To ascertain whether the intervention improves the generic health related quality of life the EuroQuoL (EQ-5D) will be used.^{39,40} The EQ-5D was feasible in the pilot study and detects even relatively small changes.^{41,42}

(3) Change in functional disability measured as the difference in the VES-13-Score⁴³ 6 months from baseline minus baseline (T1–T0) and 9 months from baseline minus baseline (T2–T0): To ascertain whether the intervention improves functional disability, the activities of daily living will be assessed. In the pilot study the WHO DAS-II was found not to be feasible. In the main study the Vulnerable Elderly Survey, 13 items (VES-13) will be used.⁴³ The VES-13 predicts death and functional decline in vulnerable elderly patients,⁴³⁻⁴⁵ encompasses physical and instrumental activities of daily living and is feasible to use (pers. comm. Dr. [name], geriatrician, VES-13 use in the German PRISCUS-project; pers. comm. [name]: VES-13 use in the Maastricht multimorbidity project).

(4) Change in all cause hospitalisation: To ascertain whether the intervention improves all cause hospitalisation of patients, hospital days are counted irrespectively of reasons for admission.

(5) Change in medication adherence: To determine whether the intervention improves the medication adherence the following outcomes will be measured:

- Change in observed adherence measured as the difference between intake (*patient's interview*) and prescribed medication (CRF reported by physician's) 6 months from baseline minus baseline (T1–T0) and 9 months from baseline minus baseline (T1–T0)

- Discrepancy score, DS (Sum of all differences in drug, time of intake, frequency and dose) / Sum of all prescriptions, $AS < 0.8$ or $> 0.2 = 1$
- Drug Score (DS, Sum of all drugs taken/sum of all prescriptions), $DS < 0.8$ or $DS > 1.2 = 1$ ⁴⁶
- Dose Score, (DoS, Sum of all daily doses taken/sum of all prescriptions), $DoS < 0.8$ or $DoS > 1.2 = 1$ ⁴⁶
- Regimen Score (RS, actual frequency of intake per day / prescribed frequency per day), $RS < 0.8$ or $DS > 1. = 1$ ⁴⁶
- Change in self-reported adherence measured as the difference in the Morisky-Score⁴⁷ 6 months from baseline minus baseline (T1–T0) and 9 months from baseline minus baseline (T2–T0)

5) Change in perceived future life expectancy reflects concepts of will to life or years of desired life [YDL] measured as the difference of the three items future expectation / expected lifetime duration / desired lifetime duration in the interval 6 months from baseline minus baseline (T1–T0) and 9 months from baseline minus baseline (T2–T0): Desired and expected life time duration are considered to be sensitive for personal experiences and scientific influences,⁴⁸ as well as indicating well being and positive life evaluation.⁴⁹ Moreover it is argued that YDL itself reflects mortality on the long run. Thus, if our intervention effects change in YDL, one might argue that participants consider the intervention as relevant in relation to their own life expectancy and life quality.

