In- and exclusion criteria for trial sites (practices)	
Inclusion criteria
 
 - General practice cares for patients covered by statutory health insurance and is active in primary care - Specialist doctor for general practice or internal medicine, or doctor with no specialist field. - Practice has internet access - Investigator's agreement to fulfil the contractual obligations arising from the trial - Investigator's agreement to the training of a HCA from the practice for the intervention, as required by the trial 
Exclusion criteria
 
 - Practice focuses on unconventional medical treatments - Practice focuses on special indications (e.g. HIV)
In- and exclusion criteria for patients	
Inclusion criteria:
 
 - Age ≥ 60 and - ≥ 3 chronic diseases affecting ≥ 2 organ systems, requiring pharmaceutical treatment and - ≥ 5 long-term prescriptions with systemic effects and - Health care provided by GP (at least one contact in most recent quarter) and - Patient is legally competent to sign any documents and - Ability to understand and participate in trial of own free will, to fill out questionnaires and participate in telephone interviews as well as - Written informed consent to participate in trial 
Exclusion criteria:
 
 - Diseases cause life expectancy of < 12 months - Abuse of alcohol or illegal drugs and visible clinical signs or symptoms thereof - Cognitive disability that prevents trial participation (MMSE < 26) - emotional stress that prevents participation in trial - Participation in a clinical investigation within the last 30 days
Outcomes	
Primary outcome: difference in Medication Appropriateness Index (MAI)-Score 6 months from baseline minus baseline (MAI T1–T0)
 
Secondary outcomes: MAI T2-T0 and the difference in the following scores 6 and 9 months from baseline minus baseline (T1-T0 and T2-T0): EQ-5D, VES-13, all cause hospitalisation, medication adherence (observed: AS, DS, DoS, RS, self-reported: Morisky-Score), MRCI, BMQ, pain assessment (grade of severity of chronic pain in accordance with M. von Korff, J. Ormel et al. 1992), satisfaction with shared decision making (MSH), patient's future expectation, expected / desired lifetime duration, cognitive dysfunction (VFT), depression (GDS)

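### The Discrepancy Score cut-off is true for every possible value, so the dichotomised score is constant and cannot show an intervention effect

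*Protocol*

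**What the plan says.** Protocol 8.1.2, item (5), sets out how a change in medication adherence is measured. Observed adherence compares what the patient reports taking with what the physician documents as prescribed, and is summarised in four scores.

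- The first is the "Discrepancy score, DS (Sum of all differences in drug, time of intake, frequency and dose) / Sum of all prescriptions", with the cut-off "Sum of all prescriptions, $AS < 0.8$ or $> 0.2 = 1".
- The second is the "Drug Score (DS, Sum of all drugs taken/sum of all prescriptions), $DS < 0.8$ or $DS > 1.2 = 1".
- The Dose Score is also a taken/prescribed ratio and is coded 1 if "DoS < 0.8$ or $DoS > 1.2 = 1".
- The Regimen Score divides actual by prescribed daily intake frequency. Its lower limb is at 0.8. Its upper limb names DS instead of RS, and the number breaks off after the decimal point.

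The synopsis (1.4) lists the adherence outcomes as "medication adherence (observed: AS, DS, DoS, RS, self-reported: Morisky-Score" and says they are analysed as "the difference in the following scores 6 and 9 months from baseline minus baseline (T1-T0 and T2-T0". Section 12.2 applies the primary multilevel approach to the secondary endpoints and reserves confirmatory interpretation for the primary analysis. No other section gives a different cut-off for AS.

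**The concern.** The Drug and Dose Scores are ratios that equal 1 when intake matches prescription, so a two-sided band from 0.8 to 1.2 makes sense for them. The Discrepancy Score counts differences. It equals 0 when intake matches prescription, cannot be negative, and grows as agreement worsens. A lower limb that flags small values has no place in such a score, because it flags the best agreement. Joined by *or* to an upper limb at 0.2, it leaves no value unflagged.

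AS has content that the other scores do not replace. It is the only one of the four observed scores that counts time of intake. It also does not let opposite errors cancel. With 8 prescriptions, a patient who omits one drug and takes one unprescribed drug has a Drug Score of 8/8 = 1.0. Counting one difference for each, the Discrepancy Score is 2/8 = 0.25.

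A program that follows the protocol literally would produce a variable with no information. A program that departs from it would have to choose a threshold that the protocol does not state, possibly with data in hand.

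**Working it through.** No sample size, power or error rate is involved, so there is no stated figure to reproduce. The check evaluates the coding rule itself.

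**Inputs (Protocol 8.1.2).** AS = d / p, where d is the number of differences and p the number of prescriptions, so AS ≥ 0. Code = 1 if AS < 0.8 or AS > 0.2.

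**Step 1, logic.** A value escapes code 1 only if both limbs fail, that is if AS ≥ 0.8 and AS ≤ 0.2. No number meets both conditions.

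**Step 2, enumeration.** Every fraction d/p was formed with p = 1 to 30 and d = 0 to 4p + 40 (four kinds of difference per prescription, plus room for unprescribed drugs). This gives 1,849 distinct values from 0 to 44. All 1,849 receive code 1.

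**Step 3, example.** Take p = 8, the median in the cross-sectional study described in section 2.1. The table compares the printed rule with other readings one might consider.

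| d | AS | As printed | AS > 0.2 only | < 0.8 or > 1.2 | < 0.2 or > 0.8 | Between 0.2 and 0.8 |
|---|---|---|---|---|---|---|
| 0 | 0 | 1 | 0 | 1 | 1 | 0 |
| 1 | 0.125 | 1 | 0 | 1 | 1 | 0 |
| 2 | 0.25 | 1 | 1 | 1 | 0 | 1 |
| 6 | 0.75 | 1 | 1 | 1 | 0 | 1 |
| 8 | 1.0 | 1 | 1 | 0 | 1 | 0 |
| 10 | 1.25 | 1 | 1 | 1 | 1 | 0 |

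The band copied from the sister scores (fifth column) and the swapped limbs (sixth) both flag full agreement. Reading *or* as *and* (last column) leaves the worst values unflagged. Only the one-sided rule separates low from high discrepancy in a consistent direction.

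**Step 4, consequence for the code.** The coded value is 1 at T0, T1 and T2 for every patient. So T1–T0 = 1 − 1 = 0 and T2–T0 = 1 − 1 = 0 for everyone. The variance of the change is 0 and the between-group difference is 0 by construction, whatever the intervention does.

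**Step 5, consequence for the score.** The ratio d/p itself varies (0 to 1.25 in the table), and its change can be modelled as section 12.2 describes.

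**Step 6, where the figures may come from.** The sister scores tolerate a deviation of 0.2 from their ideal value of 1. The same tolerance around an ideal value of 0 gives AS > 0.2. If the 0.8 was meant for the complement, then 1 − AS < 0.8 is the same statement as AS > 0.2. Both are conjectures about intent. The protocol does not confirm either.

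**The case against.** **The outcome may not be lost at all.** The synopsis speaks of differences in scores, and the model in 12.2 is one for mean differences in a change score. On that reading the continuous ratio is analysed and the faulty cut-off is never used. This stands as a limit: zero variance applies to the 0/1 code only. It does not remove the point, because the protocol prints a code for each observed score and never says which version is analysed.

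**The meaning of code 1 is not stated.** It is inferred from the sister scores, where 1 marks values outside the tolerated band. That inference is reasonable, but a reader who says that all patients are classed as non-adherent goes one step beyond the text.

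**The printed characters may be unreliable.** The damaged Regimen Score line shows that this list has slips, from drafting or from conversion of the file. But the obvious misreading, 0.2 for 1.2, would turn the rule into the fifth column of the table, which still codes full agreement as 1.

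**A reader might infer that nine-month observed adherence is not analysed.** The sentence in 8.1.2 labels both contrasts alike: "6 months from baseline minus baseline (T1–T0) and 9 months from baseline minus baseline (T1–T0". The documents do not support that inference. The same sentence names nine months, the synopsis gives T2–T0, section 3 sets adherence at six and nine months, section 4 measures all outcomes at T2, and Table 1 schedules both medication sources at T2. The label is a slip. The DS heading on the Discrepancy Score is one too, since section 15.1 assigns AS to the Discrepancy Score and DS to the Drug Score.

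**The weight is limited.** The adherence objective in section 3 is also served by the Drug, Dose, Regimen and Morisky scores, none of which uses the AS rule. This stands and bears on severity.

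**Conclusion.** The cut-off for AS is wrong as written: it assigns the same code to all attainable values, full agreement included. The dichotomised AS therefore cannot show an intervention effect of any size. This conclusion rests on the printed text and on AS being compared with both limbs joined by *or*. It needs no assumption about the data.

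The consequence is confined to the code. The continuous AS remains usable, both raw inputs are collected at every visit, and the score can be derived again at any time. One of five adherence measures is affected, none of them confirmatory. The primary endpoint and the sample size are untouched. The severity is minor to moderate, and it would be an overstatement to treat this as a threat to the trial's main result or to the adherence objective as a whole.

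**What to change.** In Protocol 8.1.2, item (5):

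1. Delete the lower limb so that the rule reads AS > 0.2 = 1. This is the only printed limb that fits a score with ideal value 0. The sponsor should confirm the threshold before the data are analysed, since the document does not prove what was intended.
2. State that code 1 means non-adherent.
3. State whether the score or the code is analysed, for example with the continuous AS as the main version, which suits the model in 12.2, and the code as a supplement.
4. As clerical corrections, use AS throughout for the Discrepancy Score and DS only for the Drug Score, relabel the nine-month contrast T2–T0 to match the synopsis, and complete the upper limb of the Regimen Score with the right abbreviation and a full number.

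The cost is a few lines of text, carried into the analysis plan and the derivation program. No new data, visits or patients are needed.

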The statistical analyses of the secondary endpoints will use the same multilevel approach as the primary analysis. All statistical tests will be two-sided at the significance level of $\alpha=0.05$. Because no adjustments for multiple endpoints are planned, findings will be interpreted with caution in view of the number of statistical tests undertaken. Only the result of the primary efficacy analysis will be interpreted in a confirmatory manner. Confirmatory subgroup analyses are not planned. No interim analysis with regard to efficacy will be done.

A complete case analysis will be performed. If any practices or patients are lost to follow-up, analyses will be done replacing the missing follow-up data with the last available or baseline data carried forward for that practice or patient.

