12.3 Sample size

Sample size was calculated using the primary endpoint, the change in MAI score from baseline (T0) to 6 months after baseline (T1), i.e. MAI T1–T0. Because high MAI scores indicate inappropriate prescriptions, a negative difference MAI T1–T0 indicates an improvement in the appropriateness of prescriptions for the target population. The MAI T1–T0 difference is assumed to be normally distributed in each treatment arm population and the variances of the group specific differences T1–T0 are assumed to be equal. In the preliminary analysis of PRIMUM pilot with a total of 60 patients from 12 practices, a mean MAI of 4.2 was observed at baseline. Three months later (i.e. 6 weeks after the intervention), the MAI in the intervention group decreased by 0.9 units, while the MAI in the control group decreased by 0.5 units. Thus, the resulting between-group difference was 0.4 in favour of the complex intervention. In a previous study of a similar patient population, between-group differences of 3 and 4 for changes in MAI from baseline to 3 and 12 months after randomisation were reported.³² However, the intervention in that study was even more intense than the intervention planned in PRIMUM. Thus, in the present study, a difference in the change values (MAI T1–T0) of at least 2 units between the treatment groups will be considered clinically relevant. In the PRIMUM pilot study, a pooled standard deviation of the MAI T1–T0 difference of 5.2 was observed. However, T1 was defined as 3 months from baseline, whereas in the present study, T1 is measured 6 months after baseline. Consequently, a greater standard deviation is expected for the MAI T1–T0 difference. Using the conservative assumption that the MAI scores at T0 and T1 are uncorrelated, we expect a standard deviation for MAI change of approximately 6 units. With this standard deviation, a between-group difference of 2 units corresponds to Cohen's effect size of $d=0.3$ and represents a small effect size.⁶³ Assuming an intraclass correlation coefficient (ICC) of 0.03 at practice level (which is also a conservative assumption because the ICC is assumed to be 0.01 in general practice setting⁶⁴) and assuming an average cluster size of 7 patients, we estimated a design effect of $DEFF = 1 + (7 - 1) \times 0.03 = 1.18$. Taking this design effect into consideration, a total of 62 practices and 434 patients (31 practices and 217 patients per treatment arm) will be required to detect a Cohen's d of 0.3 with a power of $1-\beta = 0.80$ using a two-sample t -test at a two-sided significance level of $\alpha=0.05$. The sample size calculation was performed using NCSS PASS 2008,

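### Observed adherence: section 8.1.2 attaches a 0/1 code to each ratio score, the protocol does not say whether score or code is analysed, and the code usually costs power

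*Protocol*

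**What the plan says.** Section 8.1.2, item (5), opens: "Change in medication adherence: To determine whether the intervention improves the medication adherence the following outcomes will be measured". Observed adherence compares what the patient reports taking with what the physician's case report form lists, as a change from baseline at 6 and 9 months.

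Four scores follow. The Drug, Dose and Regimen Scores divide something taken by something prescribed, so perfect agreement is 1. The discrepancy score divides the number of discrepancies by the number of prescriptions. Each definition carries a rule that yields the value 1, in the case of the Dose Score: "Dose Score, (DoS, Sum of all daily doses taken/sum of all prescriptions), $DoS < 0.8$ or $DoS > 1.2 = 1". The Drug Score has the same 0.8 to 1.2 band. The Regimen Score rule names DS instead of RS, and its upper limit looks incomplete in the text at hand. The discrepancy score rule assigns 1 to AS below 0.8 or above 0.2.

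The synopsis (1.4) lists, under differences in scores from baseline, "medication adherence (observed: AS, DS, DoS, RS, self-reported: Morisky-Score), MRCI, BMQ, pain assessment". Section 12.2 adds: "The statistical analyses of the secondary endpoints will use the same multilevel approach as the primary analysis" and "All statistical tests will be two-sided at the significance level of $\alpha=0.05". It reserves confirmatory interpretation for the primary endpoint. Section 3 names medication adherence among the secondary objectives.

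**The concern.** The 0/1 rules stand inside the endpoint definitions, and section 8.1.2 gives them no other use. Read together with the change from baseline and the multilevel model of section 12.2, the natural reading is that each ratio is coded first and the code is then differenced. The synopsis points the other way, towards differences in the scores.

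If the code is analysed, movement within either side of a cut disappears. A Dose Score rising from 0.50 to 0.75 is coded 1 at both visits, and one rising from 0.82 to 1.00 is coded 0 at both. Both patients count as unchanged.

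What is at stake is a named secondary objective and one of the desired effects in the synopsis. An insensitive measure could give a null adherence result that is then read as failure of the intended mechanism.

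**Working it through.** **Inputs.** From section 12.3: d = 0.3, ICC 0.03, 7 patients per practice, 31 practices (217 patients) per arm, two-sided alpha 0.05. All of these were set for the change in MAI. The protocol gives no effect, SD, distribution or non-adherence rate for adherence, so using them here is an assumption, and the distributions below are assumed too.

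**1. The plan's own figure.** Section 12.3 plans for an "effect size of $d=0.3$ and represents a small effect size", "with a power of $1-\beta = 0.80".
- Design effect = 1 + (7 - 1) x 0.03 = 1.18.
- Noncentrality = 0.3 x sqrt(7K / (2 x 1.18)), with 2(K - 1) degrees of freedom for K practices per arm.
- K = 30 gives 79.5% power and K = 31 gives 80.8%. The planned 62 practices and 434 patients are reproduced.

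**2. The discrepancy score rule.** Any value of 0.8 or more is also above 0.2, and any value below 0.8 meets the first condition. Every patient is coded 1 at every visit, so the change is 1 - 1 = 0.

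**3. One case by hand.** Assume a ratio with mean 0.8 and SD 0.1, T0 and T1 uncorrelated, and effective n = 217 / 1.18 = 183.9 per arm.
- SD of change = 0.1 x sqrt(2) = 0.1414. Shift = 0.3 x 0.1414 = 0.0424.
- Share coded 1: 0.500 at baseline and in controls at T1. In the intervention arm at T1 it is Phi((0.8 - 0.8424) / 0.1) = 0.336.
- Variance of the code change: control 0.25 + 0.25 = 0.500; intervention 0.25 + 0.336 x 0.664 = 0.473.
- z = (0.500 - 0.336) / sqrt(0.973 / 183.9) = 0.164 / 0.0727 = 2.26. Power = Phi(2.26 - 1.96) = about 62%.
- Uncut change: z = 0.3 x sqrt(183.9 / 2) = 2.88. Power = 82%. Almost all values lie below 1 here, so |score - 1| behaves much like the uncut ratio.

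**4. Simulation with the printed 0.8 to 1.2 window** (31 x 7 per arm, ICC 0.03, normal scores, T0-T1 correlation 0 and 0.5; power in %):

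| Assumed scenario | Change in code | Change in abs(score - 1) | abs(score - 1) with baseline covariate |
|---|---|---|---|
| Mean 0.8, SD 0.2, upward shift | 36-45 | 56-59 | 73-89 |
| Mean 0.9, SD 0.1, upward shift | 29-37 | 54-60 | 71-88 |
| Mean 1, SD narrows 0.20 to 0.15 | 58-64 | 71-81 | 97 |

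Over the scenarios run, change against change, |score - 1| gains about 4 to 35 points.

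**5. Where the gain vanishes.**
- Mean shift with the mean ratio near 1: the shift moves as many patients away from agreement as towards it. With mean 1.0, SD 0.2, correlation 0.5 and the unrounded d = 2/6 = 0.333, the share coded 1 goes from 0.317 to 0.344 and the code has 7% power. |score - 1| does hardly better.
- Strongly skewed (lognormal) score: full-scale power 88-92%. The code reaches 41-48% with 10% outside the band and 62-71% with 20%. At 40% outside it reaches 82-90%, a gain of only about 1 to 8 points for the full scale. At 60% it reaches 87-95%, a gain of about +1 to -5 points.

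**6. Change scoring is a separate loss.** In the narrowing scenario with uncorrelated visits, a normal approximation gives the code 53% power as a change but 85% as a T1 comparison. Part of any shortfall therefore comes from subtracting baseline and not from the cut.

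**7. Why not the raw ratio.** Both under- and over-intake are deviations. If intake only narrows around 1, the mean raw ratio does not move and its change has 5% power. The useful continuous measure is the distance from 1.

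**The case against.** The strongest objection is that the order of coding and differencing is inferred. No sentence makes the code the endpoint, the synopsis speaks of scores, and section 12 leaves detailed methods to an SAP that is not at hand. This stands as far as certainty goes: it would be wrong to assert that the protocol definitely analyses the code. It does not remove the point, because the protocol itself places the rules in the endpoint definitions, and one of them cannot work as printed.

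A reader might also infer that the plan's own assumptions imply a loss of 15 to 59 points. The documents do not support that. The statement "we expect a standard deviation for MAI change of approximately 6 units", the normality assumption and d = 0.3 all concern MAI. That range comes from a normal score with an assumed 10-60% outside the band. It is not a bound, it falls to nil or below for some skewed scores, and |score - 1| cannot be negative, so normality is doubtful for that measure. Nor can one say that the trial would probably miss an adherence effect.

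Finally, section 12.2 treats secondary results as non-confirmatory and calls for caution, and self-reported adherence (Morisky) carries no 0/1 rule. The objective does not rest on these codes alone. This stands and limits the severity.

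**Conclusion.** The point holds in a limited form and is minor. The analysed form of observed adherence is not fixed, and the discrepancy score rule as printed separates no patients.

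If the codes are what is analysed, the measure is usually less sensitive than it need be. Compared like with like, the distance from perfect agreement has about 4 to 35 points more power. That figure is illustrative: it rests on d = 0.3 and ICC 0.03 borrowed from MAI, on 31 practices of 7 patients per arm, and on assumed score distributions. The gain is close to zero for a mean shift around 1, and small to slightly negative for a strongly skewed score with 40-60% of patients outside the band. Baseline adjustment brings a further gain that should not be credited to dropping the cut.

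**What to change.** In section 8.1.2 and the synopsis:
- State that observed adherence is analysed on the full scale: the continuous discrepancy score, and |score - 1| for the Drug, Dose and Regimen Scores.
- Analyse the T1 and T2 values in the planned multilevel model with the baseline value as covariate, using robust or bootstrap standard errors if the scores are skewed.
- Keep the 0/1 band only as a descriptive table of percentages by arm and visit.
- Correct the coding rules of the discrepancy score and the Regimen Score. In the same edit, stop using DS for two different scores and correct the 9-month change in observed adherence, which is labelled T1-T0.

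The cost is wording only, with no new data. The small downside is that a mean distance from 1 is less familiar to clinicians than a percentage of non-adherent patients, which the descriptive table still supplies.
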